### **4.5.3 Physical Examinations**

A complete physical examination, performed at screening and other specified visits, should include an evaluation of the head, eyes, ears, nose, and throat, and the cardiovascular, dermatologic, musculoskeletal, respiratory, gastrointestinal, genitourinary, and neurologic systems. Any abnormality identified at baseline should be recorded on the General Medical History and Baseline Conditions eCRF.

Limited, symptom-directed physical examinations should be performed at specified post-baseline visits and as clinically indicated. Changes from baseline abnormalities should be recorded in patient notes. New or worsened clinically significant abnormalities should be recorded as adverse events on the Adverse Event eCRF.

Limited, symptom-directed physical examinations may be performed by a mobile nursing professional.

#### **4.5.4 Vital Signs**

Vital signs should include measurements of respiratory rate, pulse rate, and systolic and diastolic blood pressure while the patient is in a seated position, as well as tympanic temperature.

#### **4.5.5 Laboratory and Other Biological Samples**

Samples for the following laboratory tests will be sent to one or several central laboratories for analysis:

- Hematology: WBC count, RBC count, hemoglobin, hematocrit, platelet count, differential count (neutrophils, eosinophils, basophils, monocytes, lymphocytes, other cells)
- Chemistry panel (serum or plasma): sodium, potassium, chloride, bicarbonate, BUN or urea, creatinine, total protein, albumin, total and direct bilirubin, alkaline phosphatase, ALT, AST
- Plasma samples for PK analysis  
Consent for optional supplementary PK sampling (intensive schedule) will be obtained at the time of study entry (see [Appendix 2](#)).
- Nasal/nasopharyngeal swabs for virology tests (i.e., reverse transcriptase-polymerase chain reaction [RT-PCR], TCID50, genotyping)

For sampling procedures, storage conditions, and shipment instructions, see the laboratory manual.

Biological samples will be destroyed when the final Clinical Study Report has been completed, with the following exception:

- Plasma samples collected for PK analysis may be needed for PK assay development and validation; therefore, these samples will be destroyed no later than 5 years after the final Clinical Study Report has been completed.

When a patient withdraws from the study, samples collected prior to the date of withdrawal may still be analyzed, unless the patient specifically requests that the samples be destroyed or local laws require destruction of the samples. However, if samples have been tested prior to withdrawal, results from those tests will remain as part of the overall research data.

Data arising from sample analysis will be subject to the confidentiality standards described in Section 8.4.

#### **4.5.6 Patient-Reported Outcomes**

The Canadian Acute Respiratory Illness and Flu Scale (CARIFS) will be used to document the treatment benefit of baloxavir marboxil.

CARIFS is a reliable parental questionnaire and is composed of 18 questions, each with a 4-point Likert response. The questionnaire covers three domains: symptoms (e.g., cough), function (e.g., play), and parental impact (e.g., clinginess). The CARIFS is calculated as the sum of the items and measures duration of illness. Data handling conventions will be defined and described in the statistical analysis plan.

The questionnaire will be completed in its entirety by the parent or caregiver at specified timepoints during the study (see [Appendix 1](#)). To ensure instrument validity and that data standards meet health authority requirements, the questionnaire will be administered before the parent/caregiver or patient receives any information on disease status, prior to the performance of non-patient-reported outcome (PRO) assessments, and prior to the administration of study treatment, unless otherwise specified.

Parent/caregivers will use an electronic device to capture PRO data. The electronic device and/or instructions for completing the questionnaires electronically will be provided by site staff. The data will be transmitted to a centralized database maintained by the electronic device vendor. The data will be available for access by appropriate study personnel.

### **4.6 TREATMENT, PATIENT, STUDY, AND SITE DISCONTINUATION**

#### **4.6.1 Study Treatment Discontinuation**

Patients must permanently discontinue study treatment if they experience any of the following:

- Any medical condition that the investigator or Sponsor determines may jeopardize the patient's safety if he or she continues to receive study treatment
- Investigator or Sponsor determination that treatment discontinuation is in the best interest of the patient

The primary reason for study treatment discontinuation should be documented on the appropriate eCRF. Patients who discontinue study treatment prematurely will not be replaced.

Patients will return to the clinic for a treatment completion or treatment discontinuation visit on Day 29 ( $\pm 3$  days) (see [Appendix 1](#) for additional details).

#### **4.6.2 Patient Discontinuation from Study**

Patients have the right to voluntarily withdraw from the study (or be withdrawn by their parents or caregivers) at any time for any reason. In addition, the investigator has the right to withdraw a patient from the study at any time. Reasons for withdrawal from the study may include, but are not limited to, the following:

- Patient withdrawal of assent (or withdrawal of consent by their parents or caregivers) at any time
- Study termination or site closure
- Patient or patient's parent/caregiver non-compliance, defined as failure to comply with protocol requirements as determined by the investigator or Sponsor

Every effort should be made to obtain information on each patient who withdraws or is withdrawn by the parent/caregiver from the study. The primary reason for withdrawal from the study should be documented on the appropriate eCRF. If a patient or the patient's parent/caregiver requests that the patient be withdrawn from the study, this request must be documented in the source documents and signed by the investigator. Patients who withdraw or are withdrawn from the study will not be replaced.

#### **4.6.3 Study Discontinuation**

The Sponsor has the right to terminate this study at any time. Reasons for terminating the study may include, but are not limited to, the following:

- The incidence or severity of adverse events in this or other studies indicates a potential health hazard to patients
- Patient enrollment is unsatisfactory

The Sponsor will notify the investigator if the Sponsor decides to discontinue the study.

#### **4.6.4 Site Discontinuation**

The Sponsor has the right to close a site at any time. Reasons for closing a site may include, but are not limited to, the following:

- Excessively slow recruitment
- Poor protocol adherence
- Inaccurate or incomplete data recording
- Non-compliance with the International Council for Harmonisation (ICH) guideline for Good Clinical Practice
- No study activity (i.e., all patients have completed the study and all obligations have been fulfilled)

## **5. ASSESSMENT OF SAFETY**

### **5.1 SAFETY PLAN**

The safety plan for patients in this study is based on clinical experience with baloxavir marboxil in completed and ongoing studies. There are no anticipated important safety risks for baloxavir marboxil. Please refer to the Baloxavir Marboxil Investigator's Brochure for a complete summary of safety information.

Several measures will be taken to ensure the safety of patients participating in this study. Eligibility criteria have been designed to exclude patients potentially at higher risk for serious influenza and toxicities. Patients will undergo safety monitoring during the study, including assessment of the nature, frequency, and severity of adverse events. In addition, guidelines for managing adverse events, including criteria for dosage modification and treatment interruption or discontinuation, are provided below.

#### **5.1.1 Internal Monitoring Committee**

An IMC will review the clinical study data at regular intervals as defined in the IMC charter. Should a safety concern be identified, a treatment arm or the entire study may be suspended or discontinued, as appropriate.

#### **5.1.2 Management of Patients Who Experience Adverse Events**

Baloxavir marboxil is administered as a single-dose treatment, so no dose modification or treatment discontinuation is possible. However, the study medication can still be suspended or the patients can be discontinued if adverse events are considered to be related to the study medication (baloxavir marboxil or oseltamivir) in patients who experience toxicity considered to be related to oseltamivir.

### **5.2 SAFETY PARAMETERS AND DEFINITIONS**

Safety assessments will consist of monitoring and recording adverse events, including serious adverse events and adverse events of special interest, performing protocol-specified safety laboratory assessments, measuring protocol-specified vital signs, and conducting other protocol-specified tests that are deemed critical to the safety evaluation of the study.

Certain types of events require immediate reporting to the Sponsor, as outlined in Section [5.4](#).

### **5.2.1 Adverse Events**

According to the ICH guideline for Good Clinical Practice, an adverse event is any untoward medical occurrence in a clinical investigation patient administered a pharmaceutical product, regardless of causal attribution. An adverse event can therefore be any of the following:

- Any unfavorable and unintended sign (including an abnormal laboratory finding), symptom, or disease temporally associated with the use of a medicinal product, whether or not considered related to the medicinal product
- Any new disease or exacerbation of an existing disease (a worsening in the character, frequency, or severity of a known condition) (see Section 5.3.5.8 and Section 5.3.5.9 for more information)
- Recurrence of an intermittent medical condition (e.g., headache) not present at baseline
- Any deterioration in a laboratory value or other clinical test (e.g., ECG, X-ray) that is associated with symptoms or leads to a change in study treatment or concomitant treatment or discontinuation from study drug
- Adverse events that are related to a protocol-mandated intervention, including those that occur prior to assignment of study treatment (e.g., screening invasive procedures such as biopsies)

### **5.2.2 Serious Adverse Events (Immediately Reportable to the Sponsor)**

A serious adverse event is any adverse event that meets any of the following criteria:

- Is fatal (i.e., the adverse event actually causes or leads to death)
- Is life threatening (i.e., the adverse event, in the view of the investigator, places the patient at immediate risk of death)

This does not include any adverse event that, had it occurred in a more severe form or was allowed to continue, might have caused death.

- Requires or prolongs inpatient hospitalization (see Section 5.3.5.10)
- Results in persistent or significant disability/incapacity (i.e., the adverse event results in substantial disruption of the patient's ability to conduct normal life functions)
- Is a congenital anomaly/birth defect in a neonate/infant born to a mother exposed to study drug
- Is a significant medical event in the investigator's judgment (e.g., may jeopardize the patient or may require medical/surgical intervention to prevent one of the outcomes listed above)

The terms "severe" and "serious" are not synonymous. Severity refers to the intensity of an adverse event (e.g., rated as mild, moderate, or severe, or according to National Cancer Institute Common Terminology Criteria for Adverse Events [NCI CTCAE]; see

Section 5.3.3); the event itself may be of relatively minor medical significance (such as severe headache without any further findings).

Severity and seriousness need to be independently assessed for each adverse event recorded on the eCRF.

Serious adverse events are required to be reported by the investigator to the Sponsor immediately (i.e., no more than 24 hours after learning of the event; see Section 5.4.2 for reporting instructions).

### **5.2.3 Adverse Events of Special Interest (Immediately Reportable to the Sponsor)**

Adverse events of special interest are required to be reported by the investigator to the Sponsor immediately (i.e., no more than 24 hours after learning of the event; see Section 5.4.2, for reporting instructions). Adverse events of special interest for this study are as follows:

- Cases of potential drug-induced liver injury that include an elevated ALT or AST in combination with either an elevated bilirubin or clinical jaundice, as defined by Hy's law (see Section 5.3.5.6)
- Suspected transmission of an infectious agent by the study drug, as defined as follows:

Any organism, virus, or infectious particle (e.g., prion protein transmitting transmissible spongiform encephalopathy), pathogenic or non-pathogenic, is considered an infectious agent. A transmission of an infectious agent may be suspected from clinical symptoms or laboratory findings that indicate an infection in a patient exposed to a medicinal product. This term applies only when a contamination of the study drug is suspected.

## **5.3 METHODS AND TIMING FOR CAPTURING AND ASSESSING SAFETY PARAMETERS**

The investigator is responsible for ensuring that all adverse events (see Section 5.2.1 for definition) are recorded on the Adverse Event eCRF and reported to the Sponsor in accordance with instructions provided in this section and in Section 5.4, Section 5.5, and Section 5.6.

For each adverse event recorded on the Adverse Event eCRF, the investigator will make an assessment of seriousness (see Section 5.2.2 for seriousness criteria), severity (see Section 5.3.3), and causality (see Section 5.3.4).

### **5.3.1 Adverse Event Reporting Period**

Investigators will seek information on adverse events at each patient contact. All adverse events, whether reported by the parent/caregiver or patient or noted by study personnel, will be recorded in the patient's medical record and on the Adverse Event eCRF.

After informed consent has been obtained but prior to initiation of study drug, only serious adverse events caused by a protocol-mandated intervention (e.g., invasive procedures such as biopsies, discontinuation of medications) should be reported (see Section 5.4.2 for instructions for reporting serious adverse events).

After initiation of study drug, all adverse events will be reported until 28 days after the last dose of study drug.

Instructions for reporting adverse events that occur after the adverse event reporting period are provided in Section 5.6.

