### **3. STUDY DESIGN**

#### **3.1 DESCRIPTION OF THE STUDY**

This is a multicenter, randomized, double-blind, active-controlled (i.e., oseltamivir) study to assess the safety, pharmacokinetics, and efficacy of baloxavir marboxil compared with oseltamivir in pediatric patients 1 to < 12 years of age with influenza-like symptoms.

This study is designed to enroll approximately 120 otherwise healthy male and female pediatric patients with influenza-like symptoms presenting within 48 hours of symptom onset.

Patients will be recruited in parallel to the following two cohorts:

- 5 to < 12 years of age (minimum 40 patients)
- 1 to < 5 years of age (minimum 20 patients)

Baloxavir marboxil will be given as a single-dose, based on body weight at screening. The approved dose for oseltamivir in pediatric patients 1 to 12 years of age is BID for 5 days, based on body weight (see Section 4.3.2.2). Either drug, along with the corresponding placebo of its comparator in this trial, will be started at the time of randomization.

Patients will be screened and randomized on Day 1 and assigned in a 2:1 ratio to receive a single oral dose of baloxavir marboxil based on body weight (2 mg/kg for patients weighing < 20 kg or 40 mg for patients weighing  $\geq$  20 kg) or oseltamivir (dose based on body weight) for 5 days. Re-screening of patients who fail to meet the inclusion and exclusion criteria will not be permitted for the same illness episode, as the time from symptom onset to treatment window is limited to 48 hours.

The study consists of two periods: a 5-day treatment period (mandatory visits on Days 1, 2, and 4) and a 24-day safety follow-up period (mandatory visits on Days 6, 10, and 29). Therefore, the total study duration for each patient will be 29 days.

During the 5-day treatment period, each patient randomized to baloxavir marboxil will receive the oseltamivir matching placebo BID for 5 days, and those patients randomized to oseltamivir will receive one dose of baloxavir marboxil matching placebo on Day 1.

[figure not shown]
The following assessments will be conducted at clinic visits: physical examination, vital signs, adverse events, concomitant therapies, clinical laboratory tests, and nasal/throat swabs. Please see [Appendix 1](#) for details concerning the timing of these assessments. In addition, pharmacokinetic (PK) samples will be collected at the timepoints indicated in [Appendix 2](#).

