### 3.2 END OF STUDY AND LENGTH OF STUDY

The end of this study is defined as the date when the last patient, last visit (LPLV) occurs or the date at which the last data point required for statistical analysis or safety follow-up is received from the last patient, whichever occurs later. The end of the study is expected to occur 29 days after the last patient has been enrolled.

The total length of the study, from screening of the first patient to the end of the study, is expected to be approximately 9 months. Given the seasonal variability of incidence and severity of influenza, the total length of the study may be extended to complete enrollment.

In addition, the Sponsor may decide to terminate the study at any time.

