#### **4.3.2.2 Oseltamivir and Placebo**

Oseltamivir will be administered orally BID (morning and evening) for 5 days. The powder for suspension will be reconstituted with water, to provide a fixed dose based on the body weight of the child.

Weight-adjusted dosing regimen for children aged 1 to 12 years, for 5 days:

- ≤ 15 kg: 30 mg BID
- ≥ 16 kg to 23 kg: 45 mg BID
- ≥ 24 kg to 40 kg: 60 mg BID
- ≥ 41 kg: 75 mg BID

The oseltamivir matching placebo powder is an oral suspension and will be administered orally BID (morning and evening) for 5 days.

Oseltamivir, or matching placebo, will be given orally 12 hours apart. If the first dose is taken after 4 pm (16:00 hours) on Day 1, the next dose will be taken in the morning of Day 2. For these patients, the 10th dose will be taken on the morning of Day 6. If the first dose is taken prior to 4 pm (16:00 hours) on Day 1, the next dose should be taken in the evening of the same day (i.e., prior to midnight on the same calendar day with a minimum of 7 hours between doses). For these patients, the 10th dose will be taken in the evening of Day 5.

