##### **5.4.2.2 Events That Occur after Study Drug Initiation**

After initiation of study drug, serious adverse events and adverse events of special interest will be reported until 28 days after the last dose of study drug. Investigators

should record all case details that can be gathered immediately (i.e., within 24 hours after learning of the event) on the Adverse Event eCRF and submit the report via the electronic data capture (EDC) system. A report will be generated and sent to Roche Safety Risk Management by the EDC system.

In the event that the EDC system is unavailable, the paper Clinical Trial Serious Adverse Event/Adverse Event of Special Interest Reporting Form provided to investigators should be completed and submitted to the Sponsor or its designee immediately (i.e., no more than 24 hours after learning of the event), either by faxing or by scanning and emailing the form using the fax number or email address provided to investigators. Once the EDC system is available, all information will need to be entered and submitted via the EDC system.

Instructions for reporting serious adverse events that occur >28 days after the last dose of study treatment are provided in Section 5.6.

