## **5.6 ADVERSE EVENTS THAT OCCUR AFTER THE ADVERSE EVENT REPORTING PERIOD**

The Sponsor should be notified if the investigator becomes aware of any serious adverse event that occurs after the end of the adverse event reporting period (defined as 28 days after the last dose of study drug), if the event is believed to be related to prior study drug treatment. These events should be reported through use of the Adverse Event eCRF. However, if the EDC system is not available, the investigator should report these events directly to the Sponsor or its designee, either by faxing or by scanning and emailing the paper Clinical Trial Serious Adverse Event/Adverse Event of Special Interest Reporting Form using the fax number or email address provided to investigators.

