## 2.4 ANALYSIS TIMING

The primary study analysis will occur when the last patient has either withdrawn or completed his or her Day 29 visit, and will be based on all available data for all patients up to and inclusive of their Day 29 assessment date, as well as safety follow-up data for patients that withdrew prior to Day 29.

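### The adverse event reporting period runs to Day 33 or 34, beyond the last scheduled contact, and the SAP sets two earlier cut-offs that conflict with it and with each other

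*Protocol*

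**What the plan says.** **Reporting rule.** Protocol 5.3.1 states that, once study drug has started, "all adverse events will be reported until 28 days after the last dose of study drug". Section 5.4.2.2 repeats it: "serious adverse events and adverse events of special interest will be reported until 28 days after the last dose of study drug". Section 5.6 gives the end of the period again, "defined as 28 days after the last dose of study drug". After that point only serious events believed related to study drug need be notified.

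**Last dose.** Protocol 4.3.2.2 plans ten twice-daily doses. If the first is taken before 16:00, the 10th "dose will be taken in the evening of Day 5"; if after 16:00, the 10th "dose will be taken on the morning of Day 6". The design is double-dummy (Protocol 3.1): "each patient randomized to baloxavir marboxil will receive the oseltamivir matching placebo BID for 5 days". The study drug row of Appendix 1 covers Days 1 to 5, and its footnote c allows for Day 6.

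**Contacts.** Protocol 3.1 describes 5 days of treatment, then 24 days of safety follow-up with visits on Days 6, 10 and 29, for a total of 29 days. Protocol 4.6.1 and Appendix 1 place the final visit on Day 29 ± 3. Nothing is scheduled later. Protocol 5.3.1 has investigators ask about adverse events whenever they are in contact with the patient. Protocol 3.2 adds: "The end of the study is expected to occur 29 days after the last patient has been enrolled".

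**Analysis.** SAP 2.4 bases the primary analysis on data "up to and inclusive of their Day 29 assessment date", plus safety follow-up for patients who withdrew earlier. SAP 4.4 says that summaries of data not collected by visit, adverse events among them, use data only as far as the last exposure date. SAP 4.5.6 sets the duration of exposure in the baloxavir arm at 1 day.

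**The concern.** Safety is the primary objective, and these passages give different answers to a basic question: over what period are adverse events counted?

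The boundary matters for collection. Inside the reporting period every adverse event must be reported; outside it, only serious events thought to be related. If the period outlasts the last scheduled contact, non-serious events that begin in its final days reach the database only when a family volunteers them.

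It also matters for analysis. An event that begins after the final visit but inside the period is reportable under the protocol, yet falls outside the SAP 2.4 cut-off. Read literally, SAP 4.4 is much stricter, since it would drop everything that begins after dosing ends. Two programmers working from the same SAP could produce different adverse event tables.

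**Working it through.** No sample-size formula applies. The check is a day count.

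**The plan's own figures.** 5 treatment days + 24 follow-up days = 29, as Protocol 3.1 states; Days 6 to 29 inclusive are 29 − 6 + 1 = 24 days. Ten twice-daily doses end on the evening of Day 5 when two are taken on Day 1, and on the morning of Day 6 when one is taken on Day 1, as Protocol 4.3.2.2 states. Both figures reproduce.

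**End of the reporting period.** Last-dose day + 28:
- last dose Day 5: 5 + 28 = Day 33
- last dose Day 6: 6 + 28 = Day 34

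**Permitted final visit.** 29 − 3 = Day 26 to 29 + 3 = Day 32.

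**Coverage and gap.** With L the day of the last dose and V the day of the final visit, contact covers V − L days after the last dose, and L + 28 − V days of the period are left over.

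| Last dose | Period ends | Final visit | Days covered after last dose | Days without scheduled contact | Share of 28 days |
|---|---|---|---|---|---|
| Day 5 | Day 33 | Day 26 | 21 | 7 | 25.0% |
| Day 5 | Day 33 | Day 29 | 24 | 4 | 14.3% |
| Day 5 | Day 33 | Day 32 | 27 | 1 | 3.6% |
| Day 6 | Day 34 | Day 26 | 20 | 8 | 28.6% |
| Day 6 | Day 34 | Day 29 | 23 | 5 | 17.9% |
| Day 6 | Day 34 | Day 32 | 26 | 2 | 7.1% |

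No visit inside the window reaches 28 days after a completed course.

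**Active baloxavir dose alone.** 1 + 28 = Day 29. A visit on Day 29 or Day 32 covers this; a visit on Day 26 is 3 days short.

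**SAP cut-offs against the protocol period.**
- SAP 2.4 (Day 29 assessment date): leaves out events that begin in the days shown in the gap column.
- SAP 4.4 (last exposure date): with last exposure on Day 5 or 6, leaves out the whole 28 days after the last dose. If baloxavir exposure is taken to end on Day 1, it leaves out 33 − 1 = 32 or 34 − 1 = 33 days in that arm.
- SAP 4.5.1 defines a treatment-emergent event by its onset relative to the start of treatment and gives no end date, so it does not settle which cut-off applies.

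**The case against.** The strongest reply is that a reporting obligation is not a contact schedule. A reader might infer that the promised safety follow-up is not delivered. The documents do not support that: the follow-up that Protocol 3.1 describes is 24 days, and the schedule provides it.

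A reader might also infer that data collection closes on Day 29. Protocol 3.2 gives that only as an expectation. Its definition of study end is the later of the last visit and receipt of the last data point needed for analysis or safety follow-up. Nor is the SAP 2.4 cut-off fixed at calendar Day 29: it is the date of that assessment, and SAP Table 2 puts no upper limit on Visit 6.

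Other safeguards are real. Protocol 5.5.1 has the investigator follow each event until it resolves or is stable, subject to loss to follow-up or withdrawal of consent, so events open at the final visit are not abandoned. Events a site hears of before Day 33 or 34 must still be reported. The single active baloxavir dose is covered by a Day 29 visit, so the shortfall in that arm depends on counting dummy doses as study drug. The study drug row in Appendix 1 supports counting them, and blinded sites could not apply a different rule by arm. The schedule is common to both arms, and Protocol 6 makes all analyses descriptive.

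It may be that 28 days was meant from Day 1, since Day 29 fits that exactly. This is an inference; the text refers to the last dose in three places, and in the oseltamivir arm the last active dose is on Day 5 or 6 in any case.

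These points limit the size of the problem. They do not remove the mismatch for new-onset events after the final visit, and none of them reconciles SAP 2.4 with SAP 4.4.

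**Conclusion.** The inconsistency stands, in moderate form. For a child who completes the blinded course, the reporting period outlasts the nominal final visit by 4 or 5 days, with a range of 1 to 8; the 8-day figure needs both a Day 6 last dose and the earliest permitted visit. Scheduled contact covers 20 to 27 days after the last dose, nominally 23 or 24. What is exposed is the capture of new-onset events after that visit.

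The larger defect is in the SAP: its two cut-offs disagree, and either one leaves out events that the protocol requires to be reported.

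This rests on two assumptions: that dummy doses count as study drug, and that the course is completed. It does not apply to a child whose only dose was on Day 1 and who attends on Day 29 or later.

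The contact gap is the same in both arms, so its effect on the between-arm comparison is limited. A reader might infer from SAP 4.4 and 4.5.6 together that adverse events would be counted for 1 day under baloxavir and for 5 or 6 days under oseltamivir. The SAP does not establish this: 4.5.6 defines a duration for the exposure summary, and no section defines the last exposure date used in 4.4. That the wording permits such a reading is reason enough to correct it.

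**What to change.** Reconcile Protocol 3.1, 3.2, 4.6.1, 5.3.1, 5.4.2.2, 5.6 and Appendix 1 with SAP 2.4 and 4.4, so that all state one adverse event period. Its length is for the sponsor to choose. Two routes would work:

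- End the reporting period at the final visit, and state the follow-up after the last dose that this gives (20 to 27 days, nominally 23 or 24).
- Keep 28 days after the last dose, and add a brief contact at the end of that period.

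On either route, say whether dummy doses count as study drug for this rule. Amend SAP 2.4 to refer to the chosen period, and replace the last-exposure-date sentence in SAP 4.4, so that every treatment-emergent event in the period is analysed, with the same rule in both arms. Changing SAP 2.4 or the protocol alone would not be enough, because SAP 4.4 would still exclude post-exposure events from the summaries.

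The first route costs only wording and a slightly shorter stated follow-up. The second costs one call per child, about 120 calls at the planned enrolment. The SAP edits are wording only.
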